#### 7.3.2 Reporting Device Deficiency

All device deficiencies (DDs) related to the identity, quality, durability, reliability, usability, safety or performance of the study device including the analysis of used or explanted study device, where applicable, shall be documented throughout the study and managed by the sponsor.

The principal investigator shall record every observed device deficiency on the "Device Deficiency" form, together with an assessment for all enrolled subjects starting from the time of enrollment through the last Follow-up visit. Each DD must be described as follows:

### **Deficiency Type:**

- Identity (Packaging/Labeling)
- Quality (Structure/Appearance)

- Durability (ability to withstand wear, pressure, or damage)
- Usability (use error, misuse, abnormal use)
- Reliability (Performs in a consistent manner)
- Safety (Impact on Patient Care)
- Performance (Functions according to the IFU)

When the deficiency was noted

If the deficiency was associated with an AE

If the deficiency might have led to:

- Adverse Effect
- Serious Adverse Device Effect

Device deficiencies shall be managed by the sponsor in accordance with written procedures for the control of non-conforming product. The sponsor shall take appropriate corrective and preventive actions to protect the safety of subjects, users and other persons.

In case of DD that could have led to SADE, the sponsor determines whether the risk analysis needs to be updated and assess whether corrective or preventive action is required.

Every attempt should be made by the Site to save or collect the defective device, and if appropriate, the packaging, for return to the Sponsor. A qualified company representative will investigate and determine root cause and corrective actions as applicable, and directives will be provided to the site if warranted.

If the site documents a DD, the site will report the event in accordance with the following parameters. It should be noted that no documents should be submitted to any regulatory agency without communicating with the Sponsor beforehand to assure accuracy and completeness of the information.

For DDs, the principal investigator shall:

- report to the sponsor, without unjustified delay, all serious adverse events and device deficiencies that could have led to a serious adverse device effect and documented in the AE CRFs as noted above.
- report to the IRB/EC device deficiencies that could have led to a serious adverse device effect, if required by the national regulations or by the IRB,
- report to regulatory authorities device deficiencies that could have led to a serious adverse device effect, as required by the national regulations, and

 supply the sponsor, upon sponsor's request, with any additional information related to the safety reporting of a particular event.

Device deficiencies that did not lead to an adverse event but could have led to a medical occurrence

- a) if either suitable action had not been taken.
- b) if intervention had not been made, or
- c) if circumstances had been less fortunate,

shall be reported as specified as stated below.

Device deficiencies shall be managed by the sponsor in accordance with written procedures for the control of non-conforming product. The sponsor shall take appropriate corrective and preventive actions to protect the safety of subjects, users and other persons.

For DDs, the sponsor shall:

- report or ensure the reporting, to the IRB by the principal investigator(s), of all serious adverse events and device deficiencies that could have led to a serious adverse device effect, if required by national regulations or by the IRB,
- report to regulatory authorities, within the required time period, all serious adverse events
  including serious health threat and device deficiencies that could have led to a serious
  adverse device effect, if required by national regulations or the CIP,
- report all relevant safety information to the DMC, if established, according to written procedures

#### 7.3.3 Regulatory Reporting and Timelines

Report by the Investigator to the Sponsor

The sponsor shall implement and maintain a system to ensure that the reporting of the reportable events as defined under Section 7.2.1 Non-Reportable Event will be provided by the investigator to the sponsor immediately, but not later than 5 calendar days after investigation site study personnel's awareness of the event.

#### Report to the IRB

Prior to initiation of the study, reporting requirements of AEs and DDs for the IRB will be verified and documented. Reporting will occur according to the requirements set forth by the involved IRB and/or national requirements.

# 8 Lost to follow up

A participant will be considered lost to follow-up if he or she fails to return for follow up visit per the standard of care of the site.

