# 3.3 Primary Endpoint

The primary endpoint of this retrospective study is the incidence of post-operative complications requiring procedural intervention within 90 days post index procedure.

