# 5 Study Population

#### 5.1 Inclusion Criteria

- 1. Patients between 22 years and 80 years old (inclusive) at time they underwent abdominal wall reconstruction utilizing Gentrix® Surgical Matrix as a reinforcement graft during the time period between November 1, 2017, and present (90 days prior to the start of the data collection).
- 2. Subject underwent abdominal wall reconstruction for a hernia(s) using Integra® Gentrix® Surgical Matrix.

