#### 6.1.4 Follow-Up Visit

The time frame for follow up visits is up to 1 year or shorter, as applicable.

Since previous visit, the patients' data to be collected at the follow-up visit(s) are:

- Post-operative complications requiring procedural intervention
- Post-operative complications (Surgical Site Occurrences)
- Surgical Site Infections (SSIs)
- · Hernia recurrence confirmed by clinical assessment
- Reoperations due to index repair

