#### 6.1.5 Study exit

The patients' data to be collected at study exit are:

Study Exit Type

Note: Completion of Worksheets/ eCRFs: Site will transcribe/transmit the above-mentioned patients' data in study worksheets & eCRFs. The patients' data will originate from existing medical and other patient records.

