#### 3.2 Secondary Endpoint

- 1. Incidence of early post-operative complications (Surgical Site Occurrences) within 90 days post index procedure (seroma, abscess, dehiscence, hematoma, wound necrosis, ileus, fistula, delayed wound healing).
- 2. Incidence of Surgical Site Infections (SSIs) within 90 days post index procedure.
- 3. Incidence of later post-operative complications occurring after 90 days post index procedure.
- 4. Incidence of hernia recurrence confirmed by clinical assessment.
- 5. Incidence of reoperation requirement due to index repair.

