#### 7. ANALYSIS POPULATION

**Enrolled**: The enrolled population includes all eligible subjects based on the defined inclusion and exclusion criteria.

**Intent-to-Treat (ITT) Population:** All subjects who are enrolled into the study, provide informed consent waiver, and receive study intervention.

**Per-Protocol (PP) Population**: All subjects in the full Analysis Set not identified as major protocol violations.

The endpoints analysis will be based on the Intent-To-Treat population. The per-protocol set will be supportive and will be used to assess the robustness of study results if neccesary. Safety analysis will be based on the Intent-To-Treat population.

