#### 9.3.1 Analysis of the Primary Endpoints

The incidence of post-operative complications requiring procedural intervention within 90 days post index procedure.willbe summarized. The proportion of subjects with the incidents will be presented.

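### No minimum observed follow-up, denominator rule or censoring is set for the 90-day and later incidences, so the reported rates depend on how subjects whose charts end early are handled

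*Protocol*

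**What the plan says.** - **Eligibility.** Protocol 5.1 requires the operation to fall between "November 1, 2017, and present (90 days prior to the start of the data collection". No section asks for a chart contact at or after day 90.
- **Length of follow-up.** Protocol 6.1.4: "The time frame for follow up visits is up to 1 year or shorter, as applicable". This sets a ceiling and no floor.
- **Loss to follow-up.** Under Protocol section 8 a participant is lost who "fails to return for follow up visit per the standard of care of the site". A subject who completes a short routine schedule and is last seen before day 90 is not lost.
- **Study exit.** Protocol 6.1.5 lists one item, "Study Exit Type".
- **Endpoints.** The primary endpoint (Protocol 3.3) is the "incidence of post-operative complications requiring procedural intervention within 90 days post index procedure". The third secondary endpoint (SAP 3.2) is the "Incidence of later post-operative complications occurring after 90 days post index procedure", with no end date. Recurrence and reoperation carry no time horizon.
- **Analysis.** SAP 9.3.1: "The proportion of subjects with the incidents will be presented". SAP 9.3.2 treats the secondary endpoints in the same way. SAP section 7: "The endpoints analysis will be based on the Intent-To-Treat population". That population is everyone enrolled and treated, with no follow-up condition.
- **Missing data.** SAP section 11 expects some endpoint data to be missing and says only that they will not be imputed. The statistical paragraph of the Protocol synopsis (1.1) refers to evaluable subjects and does not define the term.
- **Time to event.** The only such analysis is the recurrence curve in SAP 9.2.8, which is worded to cover subjects who had a recurrence.

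**The concern.** Elapsed time is not observed time. In a chart review, a patient released from care after a few weeks and a patient followed to day 90 without trouble both show no event. A crude proportion over all treated subjects does not distinguish them, and the planned exit-type table would not do so either, because the loss rule has no link to day 90.

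The problem is sharper after day 90. Time at risk there varies from almost nothing to most of a year, yet every treated subject counts equally in the denominator.

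The study has no comparator and no hypothesis, so the reported incidences are its whole result. The Protocol background quotes recurrence and wound infection rates for other biologic materials at 18.2 months. Readers will make that comparison, and a rate without its follow-up time would mislead them.

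**Working it through.** **Inputs from the documents.** About 35 subjects (Protocol 10.2, SAP 8); 90-day horizon (Protocol 3.3); follow-up of at most one year (Protocol 6.1.4); data collection of about one month (Protocol 5.4). The figure of 35 comes without a calculation, so there is no plan figure to reproduce. No event rate or share of incomplete charts is given.

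**Assumed inputs.** *p* is the true 90-day incidence, 20% here (the range 10–30% was also examined). *f* is the share of subjects whose chart ends before day 90, 10–40%. *g* is the share of those subjects' events that fall after last contact and never reach the chart, 25–100%. Underlying risk is taken as equal in both groups.

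**1. Reading A: all treated subjects in the denominator.** Expected crude incidence = p(1 − fg). The relative understatement is fg, whatever p is: from 0.10 × 0.25 = 2.5% to 0.40 × 1 = 40%. It is never negative.

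**2. Reading B: event-free subjects not seen to day 90 are dropped, and early events are kept.** Expected incidence = p(1 − fg) / [(1 − f) + fp(1 − g)].

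| f | g | Reading A | Reading B |
|---|---|---|---|
| 10% | 25% | 19.5% | 21.3% |
| 20% | 50% | 18.0% | 22.0% |
| 40% | 25% | 18.0% | 27.3% |
| 40% | 100% | 12.0% | 20.0% |

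With a true 20%, reading A falls below the truth, while reading B meets or exceeds it. As an example, for f = 40% and g = 25%, reading B is 0.20 × 0.90 / (0.60 + 0.40 × 0.20 × 0.75) = 0.18 / 0.66 = 27.3%.

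**3. In counts.** Take 5 recorded events in 35 subjects.

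| Event-free but not observed to day 90 | All treated | Dropped | All of them had events |
|---|---|---|---|
| 4 | 5/35 = 14.3% | 5/31 = 16.1% | 9/35 = 25.7% |
| 7 | 5/35 = 14.3% | 5/28 = 17.9% | 12/35 = 34.3% |

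**4. After day 90.** The window for late complications is at most 365 − 90 = 275 days. The most recently eligible subject can have only about the one month that data collection lasts.

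For recurrence, assume a constant hazard and follow-up spread evenly from *a* to 365 days. With one-year risk R and λ = −ln(1 − R)/365, the crude proportion is 1 − [(1 − R)^(a/365) − (1 − R)] / [λ(365 − a)]. For R = 20% and a = 90, this is 1 − (0.9465 − 0.8000)/0.1681 = 12.9%. For a = 30 it is 11.2%. True one-year risks of 10% and 30% appear as 6.3% and 19.7% with a = 90.

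**5. The recurrence curve.** Restricted to subjects with recurrence, as SAP 9.2.8 is worded, it must reach 100%. It therefore overstates risk and does not correct the crude proportion.

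**The case against.** **Direction.** A reader might infer that the plan counts unobserved subjects as event-free and that its incidences are biased low. The documents do not say so. Non-imputation, and the undefined term in the synopsis, also allow such subjects to be dropped, and reading B then gives nil or upward bias. This stands, and the point is therefore conditional. It does not rescue the plan, because two permissible readings give different primary results.

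**Section 8.** The lost-to-follow-up label enters no endpoint denominator. This stands: redefining it alone would not change an estimate.

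**Last-contact date.** A reader might infer that the database will lack one. The case report forms are not among the documents, and data are to be listed by study visit (Protocol 10.4.10), so a date might be derivable. What can be said is that neither document requires it or uses it in the analysis.

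**Size.** All rates above are assumed. A complication that needs a procedure normally leaves a record if it is treated at the site, so *g* could be small for the primary endpoint. Near-zero time after day 90 is forced by the calendar only for the latest operations in a window opening in November 2017; for earlier operations it depends on how long the site saw the patient. Sampling error is also wide: 5/35 has an exact 95% interval of 4.8% to 30.3%. These points limit the likely size. They do not supply the missing rule, and the interval does not reflect this error.

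**Purpose.** The study is descriptive, with no test or success threshold. This lowers the severity.

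**Conclusion.** The point holds in conditional form. The plan sets no minimum observed follow-up, no denominator for subjects whose chart ends before day 90, and no censoring for the 90-day or later endpoints.

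With the all-treated denominator as written, the 90-day incidences are understated or at best unbiased; across the assumed ranges the relative understatement is 2.5% to 40%. For late complications, recurrence and reoperation the understatement is more secure, because unequal time at risk is built into the design. If unobserved event-free subjects are dropped instead, a true 90-day incidence of 20% would be reported as 20.0% to 27.3%.

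The true size cannot be derived from the documents. All of these figures rest on assumed event rates and follow-up patterns. This should be fixed, but with no hypothesis or threshold at stake it does not invalidate the study.

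**What to change.** 1. **Protocol 6.1.5:** add the date of last documented clinical contact for every subject.
2. **SAP 9.3.1–9.3.2:** define 90-day status as complete if an event occurred within 90 days or there was a contact on or after day 90, and report the number complete. State the denominator, and either define the synopsis term for evaluable subjects or remove it.
3. **90-day endpoints:** keep the crude proportion of all treated subjects. Beside it, give a Kaplan-Meier or cumulative incidence estimate on all treated subjects, censored at last contact. For the primary endpoint add best-case and worst-case bounds, as in step 3 of the working.
4. **Late complications, recurrence, reoperation:** give the same censored estimate to one year and state the follow-up time. Do not restrict the late-complication denominator to subjects seen after day 90, since patients often return because of a problem.
5. **SAP 9.2.8:** reword so that the recurrence curve covers all treated subjects, with those free of recurrence censored at last contact.

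The cost is one data field taken from the chart and some SAP wording, settled before database lock. Reported figures may be less favourable. Censoring at last chart contact may itself be informative and can push estimates upward. For late complications, a subject last seen before day 90 still adds nothing after it. For these reasons the crude proportion should stay alongside.

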# 9 Data-Management

# 9.1 Methods for data collection and data entry

An EDC system which is a 21 CFR Part 11-compliant data capture system with eCRF designed and the study database built will be used for the purposes of this clinical investigation. The data entered into the eCRF in the EDC system will be fully source document verified (SDV), reviewed and cleaned. Queries will be issued to the site via the EDC system and are to be resolved by the investigator or his designee using the EDC system. An audit trail in the system is available for tracking all information including the site user enters, modifies or deletes the study data and query resolution.

Data review and data cleaning will be completed on a regular basis. The study data will be reviewed and cleaned to ensure that there are no outstanding data discrepancies prior to database lock. Any changes to the database after that time will require written agreement by Integra LifeSciences Corporation.

A data-management Plan is prepared to document precisely the procedures for the study database development, data review, data cleaning and query resolution.

## 9.2 Source Data Requirements

Data collection is the responsibility of the clinical trial staff at the site under the supervision of the site investigator. The investigator is responsible for ensuring the accuracy, completeness, legibility, and timeliness of the data reported.

The investigator or its delegate will perform primary data collection drawn from original documents (printed, optical or electronic document containing source data). Data to be collected for purposes of the clinical investigation must not be entered directly into the eCRF before being recorded first in the source documents. All source documentation must be available for review by the study monitor during monitor visit. Source data is defined as all information in original records, certified copies of original records of clinical findings, observations, or other activities in a clinical investigation, necessary for the reconstruction and evaluation of the clinical investigation. All

**Integra LifeSciences** 

source documents should be completed in a neat, legible manner to ensure accurate interpretation of data.

Hardcopies of the study visit worksheets will be provided for use as source document worksheets for recording data for each participant enrolled in the study. Data recorded in the electronic case report form (eCRF) derived from source documents should be consistent with the data recorded on the source documents.

Clinical data (including adverse events (AEs), concomitant medications, and device deficiency will be entered into EDC system, a 21 CFR Part 11-compliant data capture system, provided by the Sponsor. The data system includes password protection and internal quality checks, such as automatic range checks, to identify data that appear inconsistent, incomplete, or inaccurate. Clinical data will be entered directly from the source documents.

The investigator shall ensure the accuracy, completeness, legibility and timelines of the data reported in eCRF and in all required documentation. Data reported on the eCRF shall be supported by the source documents with any discrepancies being explained. Any corrections made to documents will be done according to ISO 14155 guidelines. If an item is not available or is not applicable, this fact should be indicated; no space is to be left blank. The investigator who has signed the clinical investigation plan signature page or his/her authorized designee is to personally sign the eCRFs to validate that the observations and findings are recorded on the eCRFs correctly and completely. The eCRFs are to be completed in a timely manner after the subject's visit. Failure to meet the documentation requirements may lead to the disqualification of an investigator.

#### 9.3 Confidentiality and Data privacy

Participant confidentiality and privacy is strictly held in trust by the participating investigator, their staff, and the sponsor(s) and their interventions. This confidentiality is extended to cover testing of biological samples and genetic tests in addition to the clinical information relating to participants. Therefore, the study protocol, documentation, data, and all other information generated will be held in strict confidence. No information concerning the study or the data will be released to any unauthorized third party without prior written approval of the sponsor.

All research activities will be conducted in as private a setting as possible.

The study monitor, other authorized representatives of the sponsor, representatives of the Institutional Review Board (IRB), or regulatory agencies may inspect all documents and records required to be maintained by the investigator, including but not limited to, medical records (office, clinic, or hospital) and pharmacy records for the participants in this study. The clinical study site will permit access to such records.

The study participant's contact information will be securely stored at each clinical site for internal use during the study. At the end of the study, all records will continue to be kept in a secure location for as long a period as dictated by the reviewing IRB, Institutional policies, or sponsor requirements.

# 9.4 Study Record Retention

The Principal Investigator and Integra LifeSciences will maintain accurate, complete, and current records relating to participation in this study. If the Principal Investigator wishes to assign the responsibility of maintaining the study files to someone else or move them to another location, he/she should consult with Integra LifeSciences in writing regarding the change. The Principal Investigator will take measures to ensure that these essential documents are not accidentally damaged or destroyed.

Upon study completion, the investigator on one hand and Integra LifeSciences on the other hand will maintain all study records for the minimum time required by the US law and regulation and in accordance with 21 CFR 812, Subpart G.

# 10 Statistical Considerations

The detailed analyses methods will be described in the Statistical Analyses Plan (SAP).

#### 10.1 Statistical Hypotheses

This is a retrospective, single-arm, single center post-market study to capture existing clinical performance data to confirm the continued performance of the Gentrix® Surgical Matrix. A formal hypothesis does not apply to this study. Subjects from that consecutive series will be included in the study based on the defined inclusion and exclusion criteria.

#### Primary Endpoint(s):

The primary endpoint of this retrospective study is the incidence of post-operative complications requiring procedural intervention within 90 days post index procedure.

